12.4 Collection and Recording of Adverse Events

12.4.1 Collection Period For All Cohorts

For this study, the timelines below apply after each study-administered vaccine:

- Solicited AEs (all grades) will be collected from Day 1 (vaccine administration) through 7 days post study vaccination.
- Unsolicited AEs will be collected as follows:
 - Any unsolicited AEs that are Grade 3 or higher will be collected from randomization/allocation through vaccination administration.
 - All unsolicited AEs (all grades) will be collected from Day 1 through Day 28.

- Any flares of a secondary autoimmune disease will be reported as an unsolicited AE (all grades) and will be collected from Day 1 through the end of the participant's study participation.
- AESIs will be collected as follows:
 - Pericarditis/myocarditis events will be collected in all treatment arms. NCI-CTCAE Grade 2 or higher myocarditis and pericarditis events from Day 1 through the end of the participant's study participation.
 - New onset of pIMDs will only be collected in arms where the Sanofi-GSK COVID-19 Vaccine is administered. All grades will be collected from Day 1 through the end of the participant's study participation.
- SAEs, MAAEs, and NOCMCs will be collected from Day 1 through the end of the participant's study participation, regardless of NCI-CTCAE grade.
- COVID-19 diagnoses (all grades) confirmed by molecular COVID-19 testing will be collected from Day 1 through the end of the participant's study participation.

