8.1 Adult Stage 1 Study Procedures

8.1.1 Visit Windows

Appendix 20.1, [Table 17](#) presents the Schedule of Events for participants in Adult Stage 1. The visit windows are defined below:

- Screening until Randomization/Allocation: up to 21 days from time of obtaining informed consent until the participant is determined to meet study entry criteria (allocation for Cohort C) or randomization (for Cohorts A and B).
- Randomization: phone visit that must occur at least 7 days prior to administration of the additional homologous vaccine dose at the Baseline/Week 0 visit for Cohorts A and B.
 - See Section 8.1.2.4 Randomization/Allocation for more details on Randomization visit activities.
- Baseline (Week 0/Day 1)
 - See Section 8.1.3 Baseline (Week 0/Day 1) Visit for more details on Baseline visit activities.
- Week 1: Vaccine Diary Review Phone Visit (Day 8 – Day 12)
- Week 4: (+/- 1 week)
- Week 12: (+/- 2 weeks)
- Week 24: (+/- 2 weeks)
- Week 36: (+/- 2 weeks)
- Week 48 (End of Study): (+/- 2 weeks)

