8.1.4.4 Clinical Laboratory Assessments

Blood and urine for the clinical laboratory assessments listed below will be collected per Section 20.1 Schedule of Events. The results will be evaluated for safety by the site investigator. Abnormal tests that meet grading and reporting criteria will be reported as adverse events (See Section 12.3 Grading and Attribution of Adverse Events).

- **Local Laboratory Assessments**
 - **Pregnancy Testing (Women of Childbearing Potential Only).** Urine pregnancy test at Screening and Baseline/Week 0 visit.
 - **Molecular COVID-19 Testing** Baseline/Week 0/Day 1 molecular COVID-19 Testing can be collected and run and the results reported by a community-based laboratory (national chain pharmacy, Local MD office, State or Local Government run testing center, Urgent Care Center) not listed on the 1572. This test must be performed within the 48 hours prior to the Baseline/Week 0/Day 1 visit. For additional details, please see the ACV01 Manual of Procedures.
- **Central Laboratory Assessments**
 - **Hematology**, including complete blood count (CBC) with differential.
 - **Blood Chemistry** including CMP, eGFR.

- **Detection of antibodies against SARS-CoV-2 Spike protein (IgG)** using the Roche Elecsys® Anti-SARS-CoV-2 S electrochemiluminescence immunoassay intended for qualitative and semi-quantitative detection of antibodies to SARS-CoV-2 spike protein (RBD) in human serum.
- **Disease-specific laboratory assessments:**
 - RA participants only
 - C-Reactive Protein (CRP)
 - SLE participants only
 - Anti-dsDNA, C3, C4
 - Random urine protein-creatinine ratio
 - Urinalysis: microscopic
 - B-cell depleting therapy participants only
 - If on CD20 depleting agent, CD19+ B cells
 - Pemphigus participants only
 - Anti-desmoglein 1/3 IgG autoantibodies by ELISA

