20.1 Schedules of Events

Table 17. Schedule of Events for Adult Stage 1

Visit Number	PRESCRN	SCRN	Randomization	Week 0	Week 1	Week 4	Week 12	Week 24	Week 36	EOS	ET	UNS
Description	Pre-Screening	Screening	Randomization Phone Visit	Baseline	Vaccine Diary Review Phone Visit	Week 4	Week 12	Week 24	Week 36	Week 48	Early Termination	Unscheduled
Visit Window		-21 Days	At least 7 days prior to Vaccination	Week 0/Day 1	Day 8 – Day 12	+/- 1 week	+/- 2 weeks	+/- 2 weeks	+/- 2 weeks	+/- 2 weeks		
Clinical Blood Draw (mL)	0	31	0	21	0	21	21	21	21	21	21	21
Research Blood Draw (mL)	0		0	61	0	55	55	55	55	55	55	55
Visit Draw Total (mL)	0	31	0	82	0	76	76	76	76	76	76	76
General Assessments												
Pre-Screening Informed Consent ^A	X											
Informed Consent		X										
Demographics		X										
Medical History	X	X	X									
Concomitant Medications (including contraceptives)	X	X	X			X	X	X	X	X	X	X
Comprehensive Physical Exam ^B		X										
Targeted Physical Exam ^C				X		X	X	X	X	X	X	X
Neurological Exam ^D					X		X	X	X	X	X	X
Vital Signs		X ^E		X		X	X	X	X	X	X	X
Adverse Event Assessment					X ^{F,G}	X ^{F,G}	X ^G	X ^G				
Review of initial COVID-19 vaccination record and antibody response	X ^H											
Inclusion/Exclusion Criteria assessment	X	X										
Randomization/Allocation		X ^I										
Immunosuppressive Medication Call: MTX		X ^I			X ^I							
Immunosuppressive Medication Call: MMF/MPA			X ^K			X ^K						
Vaccine Reaction Diary ^L				X	X							
Disease-Specific Assessments												
SLE												
Confirmation of 2019 ACR/EULAR or 2012 SLICC classification criteria for SLE			X									
H-SLEDAI		X ^M		X ^N		X	X	X	X	X	X	X ^U
Thanou modified SELENA-SLEDAI Flare Index				X		X	X	X	X	X	X	X ^U
RA												
Confirmation of 2010 ACR/EULAR classification criteria for RA		X										
Tender/Swollen Joint Count		X ^M		X ^N		X	X	X	X	X	X	X ^U
SSc												
Confirmation of 2013 EULAR/ACR classification criteria for SSc		X										

Visit Number	PRESCRN	SCRN	Randomization	Week 0	Week 1	Week 4	Week 12	Week 24	Week 36	EOS	ET	UNS
Description	Pre-Screening	Screening	Randomization Phone Visit	Baseline	Vaccine Diary Review Phone Visit	Week 4	Week 12	Week 24	Week 36	Week 48	Early Termination	Unscheduled
Visit Window		-21 Days	At least 7 days prior to Vaccination	Week 0/Day 1	Day 8 – Day 12	+/- 1 week	+/- 2 weeks	+/- 2 weeks	+/- 2 weeks	+/- 2 weeks		
Patient self-reported disease flare for SSc		X		X		X	X	X	X	X	X	X ^u
Modified Rodnan Skin Score		X		X		X	X	X	X	X	X	X ^u

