^aIf a site is conducting optional pre-screening rapid result/antibody testing; the site will review the pre-screening consent with the participant and obtain his/her signature prior to conducting any pre-screening activities. Pre-screening is optional for all participants. The site may send an Elecsys® Anti-SARS-CoV-2 S (RBD) sample to the central lab as one of 3 potential pre-screening tests, as outlined in the ACV01 lab manual.

^bComprehensive physical exams include the following systems (at a minimum): general appearance, skin, head/eyes/ears/nose/neck/throat, respiratory/chest, cardiovascular, abdominal, neurological, & musculoskeletal/extremities.

^cTargeted physical exams will be guided by participant complaints and prior abnormalities.

^dNeurological Exam will be conducted for all MS participants and for participants with other diagnoses who have a neurological complaint after Screening and Randomization/Allocation.

^eHeight will be collected at Screening only. Weight, temperature, pulse, and blood pressure will be collected at each visit.

^fSolicited AEs will be collected for 7 days post study vaccination. Unsolicited AEs will be collected until 28 days post study vaccination.

^gSAEs, MAAEs, NOCMCs, AESIs, COVID-19 diagnoses, and flares of a secondary autoimmune disease will be collected from Day 1 through the end of the participant's study participation.

^hEligibility confirmed by CDC card or documentation in medical records and results of response to initial COVID-19 vaccine regimen assessed by Elecsys® Anti-SARS-CoV-2 S assay.

ⁱRandomization for Cohorts A and B must occur within 21 days of Screening and at least 7 days prior to Week 0/Day 1. During the randomization visit, sites will call participants to confirm medical history and concomitant medication data still meet eligibility criteria. Participants in Cohort C will not be randomized. These participants must have study eligibility confirmed and have the Baseline/Week 0 visit occur within 28 days of Screening. Unsolicited AEs that are Grade 3 or higher will be collected for all Cohorts between Randomization/Allocation and vaccine administration.

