If a subject experiences the same AE on multiple occasions, the event will be counted once for each occurrence when reporting the number of AEs. When reporting the number of subjects experiencing the events, a subject will only be counted once if they experience at least one event within the particular SOC or preferred term. Percentages will be based on the number of subjects in the safety population. The tabular summaries will be sorted by descending frequency by SOC and preferred term (PT) in the treatment group arm.

Summary tables will be reported for treatment emergent adverse events unless otherwise indicated. An overall summary table will include:

- Total number of events, and number and percentage of subjects experiencing at least one event for the following categories:
 - AEs
 - SAEs
 - AEs related to study vaccine
 - AE leading to study vaccine discontinuation
 - AE leading to death
 - MAAEs
 - NOCMCs
 - SARS-CoV-2 infections
 - Solicited Adverse Events
 - AEs by severity

AEs classified by MedDRA SOC and preferred term will be summarized for each treatment group for each of the following:

- All AEs
- All Related AEs
- All SAEs
- All AEs leading to study drug discontinuation
- AEs by severity
- AEs by relationship to study drug

Listings of all AEs, MAAEs, and NOCMCs will be provided for the safety population.

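### All-grade unsolicited AE collection ends at Day 28, one day before the target day of the first scheduled post-vaccination safety labs, so a non-serious Week 4 laboratory abnormality may be counted or not according to draw date or site reading

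*Protocol*

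**What the plan says.** - **Collection period.** Protocol 12.4.1: "All unsolicited AEs (all grades) will be collected from Day 1 through Day 28". SAP 9.2 has the same sentence. After that, only SAEs, MAAEs, NOCMCs, AESIs, confirmed COVID-19 diagnoses and flares of a secondary autoimmune disease are collected to the end of participation.
- **Schedule footnotes (Protocol 20.1, Tables 17-22).** "Unsolicited AEs will be collected until 28 days post study vaccination". In Table 17 this footnote is attached to AE assessment at Week 1 and Week 4; later visits carry only the footnote for the long-term categories.
- **Day numbering.** Protocol 12.4.1 makes the day of vaccination Day 1: "Solicited AEs (all grades) will be collected from Day 1 (vaccine administration) through 7 days post study vaccination". Section 8.1.1 equates Baseline, Week 0 and Day 1.
- **Week 4 window.** One week either side of target, in every population and stage (Protocol 8.1.1, 8.2.1, 8.3.1, 8.4.1).
- **Laboratory tests.** CBC and chemistry are scheduled at Week 0 and next at Week 4. Week 1 is a phone contact with no clinical blood draw; the pediatric Week 1 draw is optional and mechanistic.
- **Laboratory abnormalities as AEs.** Protocol 8.1.4.4: "Abnormal tests that meet grading and reporting criteria will be reported as adverse events". Section 8.3.4.4 says the same for children. Neither sentence sets a day limit. Section 12.3.1.4 defines treatment-emergent by a rise in grade.
- **Denominator.** SAP 9.2: "Percentages will be based on the number of subjects in the safety population". SAP 9.4 leaves the laboratory analysis to a later version.

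**The concern.** The plan appears to want Week 4 laboratory abnormalities in the AE data. It sets trial-specific grades for liver tests (12.3.1.3), reports graded abnormalities as AEs, and attaches the unsolicited-AE footnote to the Week 4 visit. Yet the collection period closes before the target day of that visit.

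Take two participants with the same transient Grade 2 rise from Baseline, both seen within the window. If 12.4.1 governs, the one sampled on Day 25 has an AE and the one sampled on Day 30 does not. The later categories would not normally pick up the second: an MAAE requires a hospitalization, emergency visit or unscheduled contact (12.2.4), and an NOCMC requires a new diagnosis expected to last at least 3 months (12.2.3). Both participants are in the SAP denominator, so the second counts as event-free.

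If 8.1.4.4 governs instead, both have an AE, and 12.4.1 and SAP 9.2 are incomplete for laboratory events. Sites could reasonably read the documents either way. What is at stake is whether the count of non-serious laboratory AEs can be interpreted. The primary endpoint, sample size and stopping rules do not depend on it.

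**Working it through.** The documents give no figure for this overlap, so there is nothing to reproduce. The check is a count of days.

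**Window.** Vaccination = Day 1. Week 4 target = 1 + 28 = Day 29. Permitted days = 29 - 7 to 29 + 7 = Days 22-36, which is 15 days.

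**Permitted draw days after the cut-off.**
- Cut-off Day 28 (12.4.1, SAP 9.2): Days 29-36 = 8 days; 8/15 = 53%. The target day is outside.
- Cut-off 28 days after vaccination (footnotes) = Day 29: Days 30-36 = 7 days; 7/15 = 47%. The target day is inside.

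**From days to samples.** The share of Week 4 samples outside the period depends on actual visit days, which the documents do not give, so visit patterns have to be assumed. For the bell-shaped patterns, day d has weight Φ((d + 0.5 - μ)/σ) - Φ((d - 0.5 - μ)/σ). The share is the sum of weights after the cut-off divided by the sum over Days 22-36.

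| Assumed Week 4 timing | After Day 28 | After Day 29 |
|---|---|---|
| Even over Days 22-36 | 53% | 47% |
| Centred on Day 27, SD 2 / 3 / 4 | 23 / 32 / 38% | 11 / 21 / 28% |
| Centred on Day 29, SD 2 / 3 / 4 | 60 / 57 / 55% | 40 / 43 / 45% |
| Centred on Day 31, SD 2 / 3 / 4 | 89 / 79 / 72% | 77 / 68 / 62% |
| Vaccinated 2 days after Baseline, visit timed from Baseline, even | 6/15 = 40% | 5/15 = 33% |
| Vaccinated 3 days after Baseline, visit timed from Baseline, even | 5/15 = 33% | 4/15 = 27% |
| Every visit on Day 29 | 100% | 0% |

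The two delayed-vaccination rows reflect 8.1.3, which allows vaccination 2-3 days after the Baseline visit. Reading these shares as shares of abnormalities needs the further assumption that the chance of an abnormal result does not vary with draw day within the window.

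**Early visits.** If Week 4 takes place on Day 22, Days 23-28 (6 days) are still inside the period but come after the last visit marked for unsolicited AEs. For visits spread evenly over Days 22-28 the mean is (6+5+4+3+2+1+0)/7 = 3 days, or 3/28 = 11% of the period; the maximum is 6/28 = 21%.

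**The case against.** The strongest objection is that the documents do not clearly exclude late results. Section 8.1.4.4 refers to the grading section (12.3), not to the collection period, and has no day limit. Section 12.3.1.4 also allows comparison with the last post-Baseline value, which with scheduled labs first arises at Week 12, well past Day 28. This stands, and it is why the conclusion is that recording may vary rather than that events are lost. It does not remove the problem: 12.4.1 and SAP 9.2 state a limit that, if followed, drops these events, and nothing says which text prevails.

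Three stronger readings are tempting but not supported:

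- **About half of Week 4 laboratory abnormalities are missed.** The 8/15 and 7/15 are shares of permitted calendar days, not of abnormalities.
- **Late abnormalities escape safety collection altogether.** They fall outside all-grade unsolicited AE collection only. The long-term categories continue, the values stay in the database, and the site investigator reviews them for safety (8.1.4.4).
- **The proportion with a vaccine-related AE is understated, and arms with late visits look safer.** All solicited AEs are attributed to vaccine (12.3.2), so a participant with any solicited reaction already counts. A missed laboratory event changes that proportion only if it was judged related and the participant had no other related AE. All arms follow the same windows, and no difference in timing between arms is shown.

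On early visits, symptoms with onset up to Day 28 are in scope by date, and 12.4.3 lets AEs be found by interview or spontaneous complaint at any time. What remains is a prompt that is missing and some delayed recall.

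**Conclusion.** The mismatch is real. Under 12.4.1 and SAP 9.2, 8 of 15 permitted draw days for the first scheduled post-vaccination CBC and chemistry, including the target day, fall after all-grade unsolicited AE collection ends; under the schedule footnotes it is 7 of 15. The one-day difference between the two cut-offs alone decides whether an on-target sample is in or out. Because 8.1.4.4 and 8.3.4.4 set no day limit, a non-serious Week 4 abnormality may be recorded or not according to draw date or site reading.

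The day counts follow directly from the documents, for vaccination on the Baseline day. The share of abnormalities affected does not: it is roughly 11-89% under the assumed patterns with some spread, and 0% or 100% if every visit is on Day 29. The finding concerns scheduled tests; an unscheduled visit may produce earlier results. It bears on the non-serious laboratory AE summaries. It should be corrected, since the current SAP specifies no laboratory analysis that would make up for it.

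**What to change.** 1. Use one cut-off for symptomatic unsolicited AEs in Protocol 12.4.1, the schedule footnotes and SAP 9.2: either Day 28 or 28 days after vaccination.
2. Add to 12.4.1 and SAP 9.2 that treatment-emergent graded abnormalities in the scheduled Week 4 sample are recorded as AEs whatever the in-window draw day, and cross-refer from 8.1.4.4 and 8.3.4.4.
3. Report laboratory AEs with participants who have a Week 4 sample as the denominator.
4. When the Week 4 visit precedes the cut-off, ask at the next contact about AEs with onset up to the cut-off.

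Extending the period for all unsolicited AEs to the Week 4 visit when that is later would be simpler to write, but it is not advised. It would make the symptom period 28 to 36 days long according to visit date (8/28 = 29% longer at most), which moves the dependence on visit date from laboratory events to symptoms.

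The cost is a few sentences in the protocol and SAP, slightly more AE recording, and some delayed recall for early visits. No new visit or test is needed.

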In addition, recently published data, consistent with the investigators experience, show that many autoimmune disease patients have significant vaccine hesitancy, based upon concerns regarding efficacy and perceived unknown safety in patients like them. In a survey of 1,531 participants, including 1,266 autoimmune disease patients enriched in SLE and rheumatoid arthritis (RA) patients, only 53% of patients reported being vaccinated or reported they would be vaccinated [24]. Within the autoimmune disease communities and patient groups, concerns are raised regarding whether a mRNA-based vaccine will be safe in those autoimmune diseases where RNA-protein complexes drive autoimmune disease pathogenesis, and whether the early infrequent autoimmune/autoinflammatory and thrombotic adverse events (AEs) that paused adenoviral-based vaccines could be harbingers of heightened concerns about autoimmune disease SAEs in individuals genetically pre-disposed to autoimmune disorders.

Vaccines using more established technologies, such as adjuvanted protein-based vaccines, may be more palatable to vaccine-hesitant individuals. Sanofi-GlaxoSmithKline (GSK) has an AS03-adjuvanted COVID-19 vaccine currently under development. While this vaccine has not been used in patients with autoimmune disease, the safety of protein or polysaccharide subunit vaccines with adjuvant, including commonly used vaccines for Hepatitis B, Pneumococcus, meningococcus, Haemophilus influenzae, and varicella zoster is well-established in this population [25]. Of note, an increased risk of narcolepsy, particularly in Sweden, was observed after an influenza vaccination campaign with Pandemrix (an AS03-adjuvanted H1N1 pandemic influenza vaccine) in 2009-2010. A similar risk of narcolepsy was not identified in other countries with AS03- or MF59-adjuvanted H1N1 pandemic influenza vaccines except for Taiwan where the incidence increased after wild-type H1N1 virus circulated in the country [26]. An EMA report in 2016 concluded that: "Based on the evidence generated so far, a hypothesis that takes into account the potential role of antigen is more likely to explain the increased risk of narcolepsy observed with Pandemrix than hypotheses that are based on a direct role for the AS03 adjuvant" [27].

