5.1.3 Risks of COVID vaccine based on the Sanofi-GSK COVID-19 Vaccine

Expected risks of the Sanofi-GSK COVID-19 Vaccine and AS03 adjuvant, based on the Sanofi Pasteur CoV2 preS dTM-AS03 adjuvanted vaccine Investigator's Brochure (v11; 25MAR2022) and the AS03 Adjuvant System Investigational Brochure (Edition 2, Version 2; 10MAR2022), include solicited injection site and systemic events. Injection site reactions may include injection site pain, injection site erythema, injection site swelling, injection site pruritus, upper limb edema, and, possibly, the extensive swelling of the vaccinated limb extending beyond the closest joint. Systemic reactions may include fatigue, nausea, diarrhea, fever, headache, malaise, myalgia, arthralgia, and chills as separate events or a combination of events.

Potential (not observed in clinical trials) class effect for all vaccines include anaphylactic reactions, vaccine-associated enhanced disease, exacerbation of pre-existing or development of new immune-mediated disease, and vasovagal reactions or psychogenic reactions.

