12.2.4 Medically Attended Adverse Event

Medically attended adverse event (MAAE) is defined as a hospitalization, emergency room visit, or an otherwise unscheduled visit to or from medical personnel for any reason that is considered possibly related or related to study vaccine.

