12.2.5 Adverse Events of Special Interest

Adverse events of special interest (AESIs) include the following:

- Myocarditis (probable and confirmed cases)
- Pericarditis

See Appendix 20.8 for cases definitions of probable and confirmed myocarditis and pericarditis according to the Centers for Disease Control and Prevention (CDC) criteria

In addition, the following AESI will be collected in the arms in which the Sanofi-GSK COVID-19 Vaccine is administered.

- New onset of potential immune-mediated diseases (pIMDs).

See Appendix 20.7. Disease flares of the underlying autoimmune disease, including new manifestation of the disease will not be captured as an AESIs. Disease flares should be reported following Section 12.4.2 Increase in Autoimmune Disease Activity.

pIMDs are a subset of AEs that include autoimmune diseases and other inflammatory and/or neurologic disorders of interest which may or may not have an autoimmune etiology. AEs that need to be recorded and reported as pIMDs, including those listed in Appendix 20.7.

However, the Investigator will exercise their medical and scientific judgment in deciding whether other diseases have an autoimmune origin (that is pathophysiology involving systemic or organ-specific pathogenic autoantibodies) and should also be recorded as a pIMD. When there is enough evidence to make any of the diagnoses mentioned in Appendix 20.7 the AE must be reported as a pIMD. Symptoms, signs or conditions which might (or might not) represent the above diagnoses, should be recorded and reported as AEs but not as pIMDs until the final or definitive diagnosis has been determined, and alternative diagnoses have been eliminated or shown to be less likely.

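### Counts of new-onset potential immune-mediated disease (pIMD) cannot be compared between vaccines, because only the Sanofi-GSK arms collect it in full

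*Protocol*

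**What the plan says.** Protocol Section 12.2.5 makes myocarditis and pericarditis adverse events of special interest (AESIs) in all arms, then adds pIMDs for one product: "In addition, the following AESI will be collected in the arms in which the Sanofi-GSK COVID-19 Vaccine is administered". Section 12.4.1 repeats the restriction ("New onset of pIMDs will only be collected in arms where the Sanofi-GSK COVID-19 Vaccine is administered") and sets grade and window: "All grades will be collected from Day 1 through the end of the" participant's time on study. Sections 12.5.1 and 12.5.2 require AESIs to be reported within 24 hours. Appendix 20.7 supplies the disease list.

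For every arm, Section 12.4.1 collects:

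- all unsolicited adverse events (AEs) from Day 1 to Day 28;
- SAEs, MAAEs and NOCMCs of any grade to the end of participation;
- flares of a secondary autoimmune disease to the end of participation;
- myocarditis and pericarditis of Grade 2 or higher to the end of participation.

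A NOCMC (Section 12.2.3) is a new diagnosis expected to last at least 3 months and to need continuing care. An MAAE (Section 12.2.4) is an unscheduled medical contact "for any reason that is considered possibly related or related to study vaccine".

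On the risk itself, Section 5.1.3 says that the potential "class effect for all vaccines include anaphylactic reactions, vaccine-associated enhanced disease, exacerbation of pre-existing or development of new immune-mediated disease". The same sentence notes that these were not observed in clinical trials. The footnote to Appendix 20.7 describes its starred conditions as AESIs potentially applicable to COVID-19 vaccines in general.

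**The concern.** The protocol treats new immune-mediated disease as a possible effect of any vaccine, yet collects it as a category in the arms of one product. All participants already have an autoimmune disease, so some new immune-mediated diagnoses can be expected whatever vaccine is given.

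Two displays would mix unequally collected events. The DSMB listing (Section 12.8.2.1) includes AESIs, and pIMDs carrying that label can appear only against the Sanofi-GSK vaccine. The SAP's AE summaries by treatment group (SAP Section 9.2) would contain late, minor pIMDs from the Sanofi-GSK arms that the other arms were never asked to record. Section 12.5.3.2 also names, as grounds for expedited reporting, an aggregate analysis showing events more often on drug than in a concurrent or historical control group. A reader making that comparison from the recorded events could take a difference in collection for a difference in risk.

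**Working it through.** **No figure to reproduce.** Neither document gives a pIMD rate or plans a test on pIMDs. The one check available is the denominator: Protocol Table 5 has 12 Adult Stage 2 arms, and 12 × 80 = 960, which matches the stated maximum.

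**Who records what.** Take a new pIMD with onset after Day 28:

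| Event | Sanofi-GSK arms (D4, E4, F4) | Other arms |
|---|---|---|
| Serious | recorded | recorded (SAE) |
| Chronic, needing continuing care | recorded | recorded (NOCMC) |
| Medically attended and judged possibly related or related | recorded | recorded (MAAE) |
| Non-serious, non-chronic, judged unrelated | recorded, all grades | not recorded |
| Idiopathic or immune-mediated myocarditis/pericarditis, Grade 1 only and meeting none of the first three rows | recorded as pIMD | not recorded |

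For example, a short-lived, non-serious facial palsy in Month 4, judged unrelated, is an AESI in Arm D4 and is not collected in Arm D2. Up to Day 28 all arms record every unsolicited AE, so the window is equal there. The disease list and the 24-hour rule still prompt sites only in the Sanofi-GSK arms.

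**Size of the artefact.** Assume equal true pIMD rates, onset spread evenly over 48 weeks (336 days), full capture in the Sanofi-GSK arms, and no effect of prompting. Let q be the share of pIMDs that qualify as an SAE, NOCMC or related MAAE. This is an assumption; the documents do not give q. Capture in the other arms is

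c = q + (1 − q) × 28/336,

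where 28/336 = 0.083. The spurious ratio, Sanofi-GSK to other, is 1/c.

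| q (assumed) | c | 1/c |
|---|---|---|
| 0 (the gap subset alone) | 0.083 | 12 |
| 0.25 | 0.25 + 0.75 × 0.083 = 0.31 | 3.2 |
| 0.50 | 0.50 + 0.50 × 0.083 = 0.54 | 1.85 |
| 0.75 | 0.75 + 0.25 × 0.083 = 0.77 | 1.30 |
| 0.90 | 0.90 + 0.10 × 0.083 = 0.91 | 1.10 |
| 1.00 | 1.00 | 1.0 |

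For a tally of events labelled as pIMD AESIs, the other arms contribute zero by rule and no ratio can be formed.

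**After a common rule.** With the same list, window and grade in all arms, c = 1 and the ratio is 1.0 whatever q is. The open adult mRNA arms (D2, D3, E2, E3, F2, F3) would supply up to 6 × 80 = 480 concurrent recipients beside up to 3 × 80 = 240 Sanofi-GSK recipients.

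**The case against.** Product-specific surveillance has a rationale in the documents. The Sanofi-GSK vaccine is under investigational use (Section 6.4), had not been used in patients with autoimmune disease, and is introduced with a discussion of AS03 and narcolepsy (Section 1.1). The mRNA vaccines are authorized or approved (Section 1.3). The class-effect sentence stands in the Sanofi-GSK risk section, and the mRNA risk section does not name new immune-mediated disease. Section 1.1 does report that "concerns are raised regarding whether a mRNA-based vaccine will be safe in those autoimmune diseases where RNA-protein complexes drive autoimmune disease pathogenesis", but as a worry in patient communities about existing disease, not about new-onset pIMDs. This explains why closer watch was placed on one product. It does not make the resulting counts comparable, and the Appendix 20.7 footnote is not limited to one product.

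It is also true that no pIMD comparison is planned and that Adult Stage 2 is not randomized (Section 3.5.1.2). Vaccine follows participant choice and vaccination history, so a comparison would be confounded even with identical collection. That stands. It limits what any display can show, but is no reason to add an avoidable ascertainment difference.

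Three stronger readings are tempting and are not supported:

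- A reader might infer that there is no concurrent comparator at all. There is one for serious, chronic and related medically attended disease, which is collected in every arm to the end of participation.
- A reader might infer an all-or-nothing contrast, with every background pIMD counted under Sanofi-GSK and none elsewhere. That would require that no event in the other arms starts by Day 28 or qualifies as an SAE, NOCMC or MAAE.
- A reader might infer that rollover turns disease from the mRNA period into Sanofi-GSK onset. Rollover screening (Section 8.2.2.3.2) updates medical history and AEs, and Table 19 repeats both at Stage 2 Week 0 before the dose. A disease still undiagnosed then is a limit of diagnosis, since Section 12.2.5 withholds the pIMD label until the diagnosis is definitive.

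**Conclusion.** The point holds as an ascertainment bias of limited scope. Between-vaccine pIMD counts are not comparable. The collection gap is non-serious, non-chronic disease judged unrelated with onset after Day 28. To this are added unequal prompting and a lower grade floor for idiopathic or immune-mediated myocarditis and pericarditis in the Sanofi-GSK arms.

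The size cannot be fixed from the documents. Under equal true rates and even onset, the spurious ratio runs from about 3.2 if a quarter of pIMDs qualify by another route to about 1.1 if nine in ten do. Many listed diseases are typically chronic, which favours the lower end, but that is a judgement and not a document figure. An imbalance in SAEs or NOCMCs is not produced by differing windows, though prompting could still influence it.

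**What to change.** 1. **Protocol.** Amend Sections 12.2.5 and 12.4.1 so that new-onset pIMDs are collected with the same list, window and grade in all open Adult Stage 2 arms. Extension to the pediatric arms is optional and would serve monitoring only, since there is no pediatric Sanofi-GSK arm.
2. **SAP.** The SAP summarizes protocol Version 3.0 and has no AESI or pIMD output. Add a rule that applies the Appendix 20.7 list to coded AE, SAE, MAAE and NOCMC terms in every arm, and tabulate by vaccine. Restrict any between-vaccine display to events collected under the same rule in all arms, and label it non-randomized and descriptive.
3. **Transition.** Flag separately any events from before the rule change and any obtained by retrospective questioning. A look-back question in mRNA arms is not equivalent to prospective collection in Sanofi-GSK arms.

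If the protocol is not amended, item 2 alone still prevents a misleading display, because terms on the list can be identified in any arm from the coded data. The cost is wording in two protocol sections, a small number of extra AESI reports and one extra table.
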